3.8.1.5 Examination at Discontinuation

At discontinuation, the investigator or subinvestigator will perform the observations, tests, and assessments shown in Table 3.8-1 as promptly as possible, within the same day if possible, after discontinuation has been decided and will record the results along with the date of visit. If at time of discontinuation, the subject or caregiver refuses any of the tests or if the investigator or subinvestigator judges that tests cannot be performed due to an emergency, only those observations, tests, and assessments that are feasible will be performed.

3.8.1.6 Follow-up Observation (Twenty-eight Days After Completion or Discontinuation of IMP Administration)

The investigator or subinvestigator will perform the observations, tests, and assessments shown in Table 3.8-1 and record the results and date of visit. These observations, tests, and assessments will also be performed in discontinued subjects unless the subject or caregiver refuses any of the tests or the investigator or subinvestigator judges that tests cannot be performed due to an emergency.

3.8.2 Safety Assessments

Evaluation points for each item are shown in Table 3.8-1.

3.8.2.1 Adverse Events

Refer to [Section 5 Reporting of Adverse Events](#).

3.8.2.2 Clinical Laboratory Assessments

In this trial, the clinical laboratory tests shown in Table 3.8.2.2-1 will be conducted by central analysis. Blood and urine samples will be collected from each subject, and the date and time of blood sampling, the date of urine sampling, and the verification of whether blood sampling was performed when the subject was in a fasted state (having fasted for at least 8 hours) will be recorded in the source documents and the CRF. Subject eligibility will be verified using the clinical laboratory test values determined at the central or local laboratory. If laboratory test values determined at the local laboratory are used for verification of subject eligibility, it must first be verified that quality control has been performed. If any of the test results provided by the central laboratory at a later date falls under the exclusion criteria, the subject will be withdrawn from the trial. For appropriate procedures for the collection, handling, and shipment of samples analyzed at the central laboratory, the separately prepared procedures should be followed. The total amount of blood to be collected for clinical laboratory tests during the trial period will be described in the ICF and explanatory materials.

The central laboratory will report the results of tests to the investigator or subinvestigator. The investigator or subinvestigator will confirm the results of tests and date and sign the clinical laboratory test report to make it an official document. The results of laboratory tests, which will be reported directly from the central laboratory to the sponsor as an electronic file, do not need to be recorded in the source documents or the CRF.

Table 3.8.2.2-1 Clinical Laboratory Assessments	
Hematology:	Serum chemistry:
Red blood cell count	ALT
White blood cell count	AST
Differential count of white blood cells (neutrophils, eosinophils, basophils, monocytes, and lymphocytes)	Alkaline phosphatase (ALP)
Platelet count	Lactic dehydrogenase (LDH)
Hemoglobin	Gamma-glutamyl transpeptidase (γ -GTP)
Hematocrit	Total protein
Prothrombin time (PT)	Total bilirubin
PT (international normalized ratio [INR])	Albumin
Activated partial thromboplastin time (APTT)	Cholesterol (total cholesterol, low-density lipoprotein [LDL] cholesterol, and high-density lipoprotein [HDL] cholesterol)
Urinalysis:	Triglycerides
pH	Blood urea nitrogen (BUN)
Protein	Creatinine
Glucose	Uric acid
Occult blood	CPK
Urobilinogen	Blood electrolytes (Na, K, Cl, Mg, Ca, P,)
Specific gravity	Blood glucose (fasting or nonfasting)
Ketone body	HbA1c (NGSP value)
	Endocrinology:
	Serum prolactin
	Insulin

3.8.2.3 Physical Examination

The investigator or subinvestigator will conduct a physical examination for HEENT (head, eye, ear, nose, and throat), chest, abdomen, urogenital organs, extremities, nerves, and skin/mucosa.

In the baseline evaluation, all the physical findings obtained on the evaluation day will be recorded in the source document and CRF. In subsequent evaluations, only information on whether an observation was made or not and the date and time of observation will be recorded in the source document and CRF. Clinically significant physical findings obtained in and after the baseline evaluation will be recorded as AEs in the source document and CRF.

3.8.2.4 Vital Signs (Blood Pressure and Pulse Rate)

After the subject has been rested, the investigator or subinvestigator will measure vital signs in accordance with the methods specified by the trial site. The results, date and time of measurement will be recorded in the source document and CRF. If the subject complained of symptoms of orthostatic hypotension before evaluation, measurement should also be performed in the supine and standing positions, in so far as possible, in the order of the supine, sitting, and standing positions.

3.8.2.5 Body Weight

Body weight will be measured using a standard measurement method (no shoes, with clothes on).

The date and results of measurements will be recorded in the source document and CRF (increments: 0.1 kg).

3.8.2.6 Twelve-lead Electrocardiography

After the subject has been placed in a resting position, the subject's ECG will be recorded using a 12-lead electrocardiograph supplied by the central ECG laboratory. The subject's eligibility will be determined on the basis of their centrally or mechanically read QTcF values. If eligibility judgment is based on the results of centrally read QTcF values, those subjects whose values at Week 10 of Trial 331-102-00088 meet the criteria (≥ 450 msec for men, ≥ 470 msec for women) will be excluded from the trial. If eligibility judgment is based on the results of mechanically read QTcF values, those subjects whose values at Week 10 of Trial 331-102-00088 meet the criteria (≥ 450 msec for men, ≥ 470 msec for women) will undergo 2 additional ECG examinations, and those with at least 1 of the 2 QTcF measurements meeting the criteria will be excluded from the trial. If QTcF results provided by the central ECG laboratory at a later date fall under the discontinuation criteria, the subject will be withdrawn from the trial. In triplicate ECG examinations, a subject will be withdrawn from the trial if at least 2 of 3 QTcF measurements meet the discontinuation criteria. ECG examinations will be performed at appropriate intervals after the subject's resting state is confirmed.

The investigator or subinvestigator will check the ECG and assess whether the result is normal or abnormal and will record the date and time of ECG, normal/abnormal judgment, and abnormal findings in the source documents and the CRF. The original of the 12-lead ECG chart will be kept in the medical record or the investigator's file. The central ECG laboratory will collect 12-lead ECG data and measure the heart rate, PR interval, RR interval, QRS interval, QT interval, and QT corrected for heart rate (QTc) [$QTcB = QT \text{ interval}/(RR \text{ interval})^{1/2}$, $QTcF = QT \text{ interval}/(RR \text{ interval})^{1/3}$], and the physician of the central ECG laboratory will assess the data.

The central ECG laboratory will report the results of analysis to the investigator or subinvestigator. The investigator or subinvestigator will confirm the results of analysis and date and sign the analysis result report to make it an official document. The investigator or subinvestigator will reconfirm the normal/abnormal judgment with reference to the analysis result report sent from the central ECG laboratory. As the results of analysis by the central ECG laboratory are reported directly from the central ECG

laboratory to the sponsor as an electronic file, they do not need to be recorded in the source documents or the CRF.

3.8.2.7 Pregnancy Test

A urine pregnancy test will be performed in WOCBP (see [Section 5.5 Pregnancy](#)), and the date of urine sampling and the result of the test will be recorded in the source documents and the CRF. The result of the pregnancy test performed at Week 10 of Trial 331-102-00088 must be obtained before starting IMP administration. If the urine test is positive, another pregnancy test will be performed using serum, and the date of blood sampling will be recorded in the source documents and the CRF. A serum pregnancy test will be performed by the central laboratory selected by the sponsor. For appropriate procedures for the collection, handling, and shipment of samples, separately documented procedures will be prepared and provided prior to the start of the trial. The central laboratory will report the results of tests to the investigator or subinvestigator. The investigator or subinvestigator will confirm the results of tests and date and sign the clinical laboratory test report to make it an official document. The results of serum tests, which will be reported directly from the central laboratory to the sponsor as an electronic file, do not need to be recorded in the source documents or the CRF.

3.8.2.8 Other Safety Assessments

The investigator or subinvestigator will record the results and the date and time of the assessments in the source documents and the CRF. The schedule for each of the assessment items is shown in Table 3.8-1.

3.8.2.8.1 Drug-Induced Extrapyramidal Symptoms Scale (DIEPSS)

By using DIEPSS, the investigator or subinvestigator will assess 9 items related to extrapyramidal symptoms on a 5-point scale on the basis of the information regarding the subject's condition after the previous assessment.

Nine items related to extrapyramidal symptoms:

Gait, bradykinesia, sialorrhea, muscle rigidity, tremor, akathisia, dystonia, dyskinesia, and overall severity

3.8.2.8.2 Abnormal Involuntary Movement Scale (AIMS)

By using AIMS, the investigator or subinvestigator will assess the severity of abnormal involuntary movement at 7 sites and 3 global judgment items on a 5-point scale and assess the dental status items “current problems with teeth and/or dentures” and “Dose patient wear dentures” as either “yes” or “no” (assessment at specified time points).

Seven sites:

“Muscles of facial expression,” “lips and perioral area,” “jaw,” “tongue,” “upper (arms, wrists, hands, fingers),” “lower (legs, knees, ankles, toes),” and “neck, shoulders, hips”

3.8.2.8.3 Barnes Akathisia Rating Scale (BARS)

By using BARS, the investigator or subinvestigator will assess the “objective,” “subjective—awareness of restlessness,” and “subjective—distress related to restlessness” for akathisia on a 4-point scale and a “global clinical assessment of akathisia” on a 6-point scale.

3.8.2.8.4 Sheehan Suicidality Tracking Scale (S-STS)

By using S-STS, the investigator or subinvestigator will assess suicidal attempt and behavior during the period since the previous visit on the basis of 22 question items.

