11	Patients whose laboratory test results at evaluation at Week 10 of Trial 331-102-00088 meet either of the following criteria for poor blood glucose control (assessed on the basis of the results from the central or local laboratory): 
 Glycosylated hemoglobin (HbA1c) of $\geq 8.0\%$ according to the global standard value (NGSP value) Fasting blood glucose level of $\geq 126 \text{ mg/dL}$ or nonfasting blood glucose level of $\geq 200 \text{ mg/dL}$
12	Patients who had neuroleptic malignant syndrome, tardive dyskinesia, paralytic ileus, or rhabdomyolysis during Trial 331-102-00088.
13	Patients who had convulsive disorders (eg, epilepsy) in Trial 331-102-00088, not including patients with febrile seizure, post-traumatic seizure, or alcohol withdrawal seizure.
14	Patients who are unable to take oral medication due to severe dysphagia.

Table 3.4.3-1 Exclusion Criteria	
15	Patients whose Sheehan Suicidality Tracking Scale (S-STS) score in Trial 331-102-00088 meets any of the following criteria, or who are judged by the investigator or subinvestigator to be at high risk of suicide: 
 • Patients with a score of 3 or 4 on any of S-STS Questions 2, 3, 4, 5, 6, or 11 • Patients with a score of 2 or more on any of S-STS Questions 1a, 7, 8, 9, 10, or 12
16	Patients whose body weight at evaluation at Week 10 of Trial 331-102-00088 was < 30 kg.
17	Patients whose body weight had fallen by ≥ 7% at Week 10 from baseline in Trial 331-102-00088.
18	Patients who were confirmed to meet the following contraindications in the package insert of REXULTI® during Trial 331-102-00088: 
 • Patients in a coma • Patients under the strong influence of central nervous system depressants, including barbiturate analogs/anesthetics • Patients receiving adrenaline • Patients with a history of hypersensitivity to the components of REXULTI®
19	Patients who are bedridden and require assistance for excretion, eating, and changing clothes
20	Women who had a positive pregnancy test result at Week 10 of Trial 331-102-00088 (women of childbearing potential only)

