3.8 Trial Procedures

The schedule of assessments is shown in Table 3.8-1, and the allowable time windows for observations, tests, and assessments are shown in Table 3.8-2.

Table 3.8-1 Schedule of Assessments

Item	Screening Period	Treatment Period							Follow-up Period
	Baseline evaluation ^a	Week 1 (Day 8)	Week 2 (Day 15)	Week 4 (Day 29)	Week 6 (Day 43)	Week 8 (Day 57)	Week 10 (Day 71)	Week 12 (Day 85)	
Informed consent	From Week 4 of Trial 331-102-00088								
Subject background information	•								
Environment investigation	←	→							→
Subject diary		←	→					←	→
Inclusion/exclusion criteria	•								
Compliance status		•	•	•	•	•	•	•	•
Safety endpoints									
Adverse events	←	→							
Confirmation of medications and therapies	←	→							
Height	△								
Body weight	△				•				•
Physical examination	△	•	•	•	•	•	•	•	•
Laboratory tests	△			•			•		•
Vital signs	△	•	•	•	•	•	•	•	•
12-lead ECG	△		•	•			•		•
Pregnancy test ^b	△								•
DIEPSS	△	•	•	•	•		•		•
AIMS	△								•
BARS	△								•
S-STS	△				•				•

Table 3.8-1 Schedule of Assessments

Item	Screening Period	Treatment Period							Follow-up Period
	Baseline evaluation ^a	Week 1 (Day 8)	Week 2 (Day 15)	Week 4 (Day 29)	Week 6 (Day 43)	Week 8 (Day 57)	Week 10 (Day 71)	Week 12 (Day 85)	
Efficacy endpoints									
CMAI	△			●					●
CGI-S	△		●	●	●		●		●
CGI-I			●	●	●		●		●
	△			●					●
	△			●					●
Other endpoints									
ADCS-ADL	△								●
MMSE	△								●

The date of starting IMP administration is designated as Day 1. IMP administration will begin no later than 10 days after the date of evaluation at Week 10 of Trial 331-102-00088.

△ The results of evaluation at Week 10 of Trial 331-102-00088 will be used except for height, for which the data obtained at screening of Trial 331-102-00088 will be used.

^aThe date of evaluation at Week 10 of Trial 331-102-00088 will be the date of baseline evaluation in this trial.

^bPregnancy test (human chorionic gonadotropin [HCG] test) will be performed for WOCBP only. If urinary test is positive, serum test will be performed.

c

d

Table 3.8-2 Allowable Time Windows for Evaluations, Tests, and Observations		
Test Point	Base Date	Allowable Time Window From the Base Date
Baseline evaluation date (at evaluation at Week 10 of Trial 331-102-00088)	Baseline evaluation date	Day -9 to Day 1
Week 1	Day 8	Day 6 to Day 10
Week 2	Day 15	Day 13 to Day 17
Week 4	Day 29	Day 27 to Day 31
Week 6	Day 43	Day 40 to Day 46
Week 8	Day 57	Day 54 to Day 60

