Week 10	Day 71	Day 68 to Day 74
Week 12	Day 85	Day 82 to Day 88
Week 14	Day 99	Day 96 to Day 106
Follow-up period	28 days after the final administration of IMP	23 to 35 days after the final administration of IMP

The date of starting IMP administration is designated as Day 1, and the day before initiation of IMP treatment is designated as Day -1.

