3.8.1.3 Environment Investigation (Day of Baseline Evaluation to Week 14 [Day 99])

If there are any changes to the subject's environment from the time of registration, the investigator or subinvestigator will record the following.

- Date of change
- Medical care category (inpatient or outpatient; if outpatient, institutionalized or care at home)
- Type of caregiver (hospital staff, care facility staff, family, or other)

3.8.1.4 Seven Days After Administration (Week 1 [Day 8]) to 98 Days After Administration (Week 14 [Day 99])

The investigator or subinvestigator will perform the observations, tests, and assessments shown in Table 3.8-1 and record the results and date of visit.

On each assessment day, the investigator or subinvestigator will provide subjects with the IMP needed for the period up until the next assessment and give them instructions to bring any unused IMPs with them to the next assessment. At visits 14 days after administration (Week 2 [Day 15]) and 84 days after administration (Week 12 [Day 85]), the investigator or subinvestigator will provide caregivers with a subject diary and give them instructions to complete the diary for 14 days before CMAI assessment and bring it with them to the next visit. In the subject diary, occurrence of daily symptoms will be recorded to evaluate the frequency of occurrence of agitation associated with dementia of the Alzheimer's type (CMAI).

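### The S-STS look-back wording is ambiguous against its visit schedule, and no planned table counts subjects with emergent ideation or behavior: a minor, cheap improvement

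*Protocol*

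**What the plan says.** **Look-back.** Protocol 3.8.2.8.4 tells the investigator or subinvestigator to "assess suicidal attempt and behavior during the period since the previous visit on the basis of 22 question items". The DIEPSS, which is also not rated at every visit, is worded differently in 3.8.2.8.1: it refers to the subject's "condition after the previous assessment".

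**Schedule.** Table 3.8-1 has treatment visits at Weeks 1, 2, 4, 6, 8, 10, 12 and 14. By cell position the S-STS is marked at baseline, Week 6 and the last treatment column. Table 3.8-2 allows "Day 40 to Day 46" for Week 6 and "Day 96 to Day 106" for Week 14. On discontinuation, 3.8.1.5 asks for the "assessments shown in Table 3.8-1 as promptly as possible".

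**Entry.** Exclusion criterion 15 removes "Patients with a score of 3 or 4 on any of S-STS Questions 2, 3, 4, 5, 6, or 11" and "Patients with a score of 2 or more on any of S-STS Questions 1a, 7, 8, 9, 10, or 12", as well as anyone the investigator judges to be at high risk of suicide.

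**Analysis.** Protocol 6.6.5.3 plans descriptive statistics for every S-STS item. SAP 9.7.3 plans them for items 2 through 14, the total and the ideation and behavior subscales, at each time point and at Week 14 LOCF. SAP 7.2 defines descriptive statistics as mean, SD, minimum, median and maximum. Tables CT-14.1 to CT-14.4 follow that pattern. SAP 9.7.2 adds a worst-postdose summary for DIEPSS, AIMS and BARS. SAP 9.3 and 9.6 count subjects who newly meet a laboratory or QTc criterion.

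**The concern.** The S-STS is a listed safety endpoint in a trial whose main objective is safety. Two things should be clear from the plan: what period each rating covers, and how many subjects became worse.

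On the first, the visit before an S-STS rating is not the visit of the previous S-STS rating. A rater who follows the sentence literally asks about a much shorter period than one who reads it as the interval between ratings. If raters differ, the scores are not comparable.

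On the second, S-STS scores are likely to be mostly zero, so means and medians say little. The useful safety result is the number of distinct subjects with new or worse ideation or behavior, and no planned table gives it.

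**Working it through.** **Reading the schedule.** The header of the last treatment column is lost in the available text. The same cell-position reading puts the CMAI at Week 4 and in that last column. Protocol 3.8.1.4 has diaries handed out at Weeks 2 and 12, when caregivers are told how to fill them in (staff "give them instructions to complete the diary for 14 days before CMAI assessment"). That places the CMAI at Weeks 4 and 14, so the last column is Week 14.

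**Look-back coverage, completers, nominal days (Day 1 to Day 99 = 98 days).**
- Literal reading: Week 4 to Week 6 is 43 − 29 = 14 days, and Week 12 to Week 14 is 99 − 85 = 14 days. Total 28 of 98 (28.6%), leaving 70 days outside any S-STS look-back.
- Previous S-STS rating: (43 − 1) + (99 − 43) = 42 + 56 = 98 of 98.

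**Recall period under the second reading, over the allowed windows.**
- Week 6: baseline may fall from Day −9 to Day 1, and there is no Day 0. Shortest 40 − 1 = 39 days; longest 46 + 9 − 1 = 54 days.
- Week 14: shortest 96 − 46 = 50 days; longest 106 − 40 = 66 days.

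**Does a score's summary determine the number of subjects?** The plan's target of 157 serves as the denominator. It reproduces: 100 ÷ (7/11) = 157.1. Take one score with all baselines 0 and compare two hypothetical sets of non-zero postdose values:

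| | Set A: 3, 4, 4, 6 | Set B: 1, 1, 1, 1, 1, 6, 6 |
|---|---|---|
| Subjects affected | 4 (2.5%) | 7 (4.5%) |
| Sum | 17 | 17 |
| Sum of squares | 77 | 77 |
| Mean = 17/157 | 0.108 | 0.108 |
| SD = √((77 − 17²/157)/156) | 0.694 | 0.694 |
| Minimum, median, maximum | 0, 0, 6 | 0, 0, 6 |

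All five planned statistics agree, yet the counts differ. The example concerns a single score at a single time point. It does not show that all item and subscale tables taken together would fail to separate these two sets.

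**Why a count must compare with baseline.** Assuming integer item scores, the numerical cut-offs of exclusion 15 alone allow up to 6 × 2 (items 2, 3, 4, 5, 6, 11) + 4 × 1 (items 7, 8, 9, 10) = 16 on the ideation subscale, and 1 on item 1a. Investigator judgement may lower this, but a non-zero baseline is possible.

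**Items.** SAP 3.5.8 builds the total and the behavior subscale from items that include 1a, 17 and 20, each scored on its own. None lies within items 2 through 14, so these three get no item summary. Items 15 and 16 enter only as the higher of themselves and items 14 and 12, which are summarized.

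**The case against.** The protocol is a translation from Japanese, so the difference between visit and assessment may be no more than variation in translation. A natural reading is the previous visit at which the scale was used, and Protocol 3.8.8 requires trained raters. Adverse events are collected throughout, and subjects are asked how they have been since the last visit (Protocol 5.2). A reader might infer from the 28-day figure that suicidality goes unassessed for 70 days. The documents do not support that: they do not show which look-back raters used. What stands is that the sentence permits both readings and that the DIEPSS wording avoids the problem.

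On counting, a reader might infer that emergent suicidality is not reported at all. That is also too strong. Suicidality adverse events are counted by subject (SAP 9.2.1, CT-8.10.17), and S-STS listings by subject are planned (PDATA-11.1 to 11.3). The other rating scales also lack subject counts, and the laboratory and QTc counts rest on preset limits that the S-STS analysis does not have. For an item whose maximum is 1, n times the mean is the count of scorers. What stands is that CT-8.10.17 captures an S-STS finding only if it was also reported as an adverse event, that distinct subjects must otherwise be counted by hand from listings, and that the S-STS lacks even the worst-postdose summary given to the other scales.

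On items, it is tempting to say that the SAP changed the protocol's analysis without recording it. The visible part of SAP 15 does not mention the change, but another part is redacted, so this cannot be established.

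**Conclusion.** The point holds as a minor, low-cost improvement, not as a demonstrated gap in safety coverage.

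1. The look-back is ambiguous: 28 or 98 of 98 nominal days for completers, depending on the reading. These figures rest on the cell-position reading of Table 3.8-1 and on nominal visit days. A discontinuation rating would add a further look-back for non-completers.
2. None of the four planned S-STS tables gives a subject count or a worst postdose value, and the summary of a given score does not determine how many subjects were affected.
3. Secondary: three stand-alone scored items (1a, 17, 20) have no item summary in the SAP although the protocol promises one for every item. This is a matter of reconciliation only.

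**What to change.** 1. In Protocol 3.8.2.8.4, define the look-back as the period since the previous S-STS assessment, in line with the DIEPSS. If data collection is complete, document which look-back the raters used. The cost is long recall in this population: 39 to 54 days at Week 6 and 50 to 66 days at Week 14.
2. In SAP 9.7.3, add the worst-postdose summary already used in 9.7.2. Add one table, by rollover group and overall, giving the number and proportion of subjects whose worst postdose score exceeds baseline, separately for the ideation and behavior subscales. Use all postdose records obtained less than 7 days after final dosing, and state this as an exception to the rule in SAP 3.4 that keeps only the last record in a window. Otherwise a positive score on Day 43 followed by a zero by Day 50, for example at a discontinuation examination that includes the S-STS, would appear only in the listing.
3. Reconcile the item lists in Protocol 6.6.5.3 and SAP 9.7.3, or record the change in SAP 15.

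All of this uses data already collected and needs no extra visits. The threshold in item 2 is a reporting convention with limits: new onset on one item offset by a fall on another, and repeat behavior scored no higher than at baseline, would not be counted and would remain in the listings only.
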